##### 6.2.1.2 Plan to destroy identifiers or a justification for retaining identifiers

At the conclusion of the data collection, after data analysis, patient identifiers will be destroyed.

#### 6.2.2 Explanation for why the research could not practically be conducted without access to and use of PHI

We will require access to patient EMR a few days prior to their Anesthesia Preoperative Clinic visit in order to ensure that they meet the inclusion criteria and not any of the exclusion criteria. If the patient in question is not eligible for study participation, no PHI will be recorded and the patient will not be approached on the day of their Anesthesia Preoperative Clinic visit.

#### 6.2.3 Explanation for why the research could not practically be conducted without the waiver or alteration of authorization

As above, PHI is needed to identify potential patients prior to their Anesthesia Preoperative Clinic visit, in order for the necessary study personnel to approach the patient on the day of their preoperative Anesthesia Clinic visit, present them with the requisite information and gauge interest in participating in the study.

### **6.3 Waiver or alteration of authorization statements of agreement**

Protected health information obtained as part of this research will not be reused or disclosed to any other person or entity, except as required by law, for authorized oversight of the research study, or for other permitted uses and disclosures according to federal regulations.

The research team will collect only information essential to the study and in accord with the 'Minimum Necessary' standard (information reasonably necessary to accomplish the objectives of the research) per federal regulations.

Access to the information will be limited, to the greatest extent possible, within the research team. All disclosures or releases of identifiable information granted under this waiver will be accounted for and documented.

## **7.0 Study Design and Procedures**

### **7.1 Study Design**

Prospective, randomized clinical trial

### **7.2 Study Procedures**

#### **7.2.1 Post-consent assignment of anesthesiologist**

After informed consent has been obtained, the anesthesiologist who will be the Chief Supervising Anesthesiologist on the day of the patient's surgery, will be notified of the name of the study patient and the date of surgery, so that one of the 3 trained anesthesiologists participating in this research study can be assigned to the patient's case.

#### **7.2.2 Day of surgery**

Randomization: The anesthesiologist assigned to administer anesthesia to the study patient will confirm the patient's study consent and ensure that the patient is still willing to participate in the study. A randomization protocol will have been created using randomization.com to randomly assign 106 patients to either the Propofol or Methohexitol groups. After the attending anesthesiologist ascertains that the patient will participate in the study, the randomization protocol will be used by a research technologist to assign the subject to a study group. The research technologist will then inform the attending anesthesiologist of which treatment the patient should receive (propofol or methohexitol).

Baseline Blood Sample Collection: Patients will not receive any premedication in the preoperative area. If they experience severe anxiety, they will be given premedication although this will exclude them from study participation. Intravenous access will be established in the preoperative area by the staff anesthesiologist using 1% lidocaine for local anesthesia if the patient requests it. This IV will be used to draw blood samples preoperatively as well as intraoperatively and to administer intravenous medications and fluids intraoperatively according to current anesthetic standards of care. An appropriately-sized blood pressure cuff will then be

applied to the ipsilateral arm. An appropriately-sized blood pressure cuff shall be defined as a cuff whose bladder length is at least 80% of the arm circumference, and whose width covers 2/3 of the distance from the elbow to the shoulder. Blood samples, for baseline analysis of AVP, All, NE and Epi levels, will be collected from the IV as follows: A tourniquet will be applied proximal to the intravenous catheter, following which 3cc of blood will be removed first to clear the 'dead space' in the intravenous line and prevent erroneous blood sampling. This blood will be discarded. A further 10cc of blood will be collected in appropriately labeled tubes (5ml in serum red top vacutainers tubes and 5ml in vacutainers tubes containing EDTA) and kept on ice until processing by our research technician, as described below. Following collection of the blood sample, 5cc of normal saline will be used to flush the line and prevent blood from clotting the catheter. A second IV will also be established in the preoperative area under local anesthesia as described above to administer intravenous medications and fluids intraoperatively according to current anesthetic standards of care.

**Operating Room Procedures:** Subjects will be attached to standard ASA monitors including electrocardiogram and pulse oximetry and noninvasive blood pressure monitor. Baseline blood pressure will be determined by taking three automated successive non-invasive blood pressure measurements every 1-2 minutes, until the systolic blood pressure (SBP) measurements is consistent (difference of no more than 10% between readings) with the patient lying in supine position. The average SBP and accompanying heart rate (HR) of these three measurements will be recorded as mean baseline values.

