Blood samples will be kept on ice at 4°C until processing. Serum samples will be allowed to clot by being left undisturbed at room temperature for 30-60 minutes. The clot will be removed by centrifuging at 1600 x g for 10 minutes @ 4°C. The liquid component (serum) will be transferred into a clean polypropylene tube using a Pasteur pipette, aliquoted, and stored @ -70°C. The plasma samples will be centrifuged at 1,600 x g for 15 minutes at 4°C and the plasma transferred to a clean microcentrifuge tube. A protease inhibitor cocktail will be added to improve the stability of desired peptides. Plasma samples will be aliquoted based on needed assay volumes and stored in -70°C until processed for data collection.

Failure to adhere to this predetermined induction and anesthetic protocol will exclude the patient from further participation in the study.

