#### **7.4.3 Method for Assigning Subject to Treatment Groups**

The randomization scheme for this study will use variable-size, random permuted blocks to ensure that the number of participants in each treatment arm is balanced after each set of  $B$  randomized participants, where  $B$  is the block size. We will use a block size of 10. Furthermore, the randomization will be stratified by gender (male/female) and drug type (ACEI/ARB). Randomization to the propofol or methohexitol arms will use 1:1 allocation. A research coordinator will access the randomization lists (developed through the website Randomization.com) stored in the secure REDCap database to randomize the participant.

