### **8.0      Subject Numbers and Statistical Plan**

#### **8.1      Number of Subjects**

The total sample size will consist of 120 participants (i.e., 60 per treatment arm). A sample size of 47 subjects per group will provide 90% statistical power to detect a difference of 0.3, between the proportion of subjects having at least one hypotension episode in the propofol group compared to the proportion in the methohexitol group, using a two-sided, chi-square test having a significance level of 0.05. However, we anticipate a drop-out rate as high as 20% for this study; therefore, we will enroll a total of 120 subjects.

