## 8.3 Statistical methods

Primary analyses will invoke an intent-to-treat paradigm, wherein all randomized subjects are included according to their randomized treatment arm, regardless of actual treatment received, compliance, etc. Data will be summarized using descriptive statistics for continuous variables (mean, standard deviation, number of observations, and percentiles) and frequency statistics (frequencies and percentages) for categorical variables. Univariate and bivariate distributions will be inspected in order to address any missing data, inconsistent responses, outliers, and data entry errors. The sample size estimates have taken into consideration a participant drop-out of 20%; however, every effort will be made during the studies to minimize any drop-out. All hypothesis tests will be two-sided and analyses will account for the two randomization stratification factors of gender and inhibitor type. All analyses will be performed using SAS software, version 9.4 (SAS Institute, Inc., Cary, NC), R software, version 3.2.2 (R Foundation for Statistical Computing, Vienna, Austria), or Stata software, version 13 (StataCorp LP, College Station, TX).

For the primary outcome of the proportion of participants having at least one hypotension episode, log-binomial regression will be used to compare the propofol and methohexitol groups, adjusting for the randomization stratification factors of gender and inhibitor type. Because this is a prospective study, the log-binomial model allows us to estimate the risk ratio rather than the odds ratio while adjusting for covariates (Wacholder, 1986).

For secondary outcome of the proportion of patients experiencing refractory hypotension, the log-binomial model as described for the primary outcome will be used to compare the treatment groups. Poisson regression will be used to compare the two treatment groups, adjusting for the randomization stratification factors, with respect to the secondary outcomes of (a) the number of vasopressor doses (i.e., ephedrine, phenylephrine and vasopressin) administered per patient and (b) the number of hypotension episodes per patient over the first 18 after treatment initiation. In the event that there is an excess of zero counts, zero-inflated Poisson (ZIP) regression will be considered (Lambert, 1992).

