## **10.0 Data and Safety Monitoring Plan**

### **10.1 Periodic evaluation of data**

We plan to perform an interim analysis of the data collected after every 30 patients enrolled in the study, until our sample size of 120 patients is achieved. We anticipate that patients receiving antagonists of the renin angiotensin aldosterone system will experience hypotension following the administration of propofol, although this is routine practice in anesthesiology without scientific literature to contraindicate practice. Our plan to treat hypotension with vasopressors is supported by the scientific literature(Mets, 2013), although we will modify our treatment plan accordingly if we deem that it is either causing hypertension or inadequate treatment of hypotension when it occurs.

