### **16.2 Feasibility of recruiting the required number of subjects**

The number of potential subjects includes any patient seen at the Anesthesia Preoperative Clinic; this generally includes most patients undergoing elective surgical procedures. We estimate one year may be required in order to recruit and collect data from 120 patients.

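### Section 7.2.2 sets up randomisation for 106 patients although the planned size is 120; with 106 and the full 20% loss, power is about 86.5% rather than 90%, at the rates that reproduce 47 per group.

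*Combined protocol and SAP*

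**What the plan says.** Section 7.2.2 (Day of surgery, randomisation paragraph) states that a randomisation scheme will be created "to randomly assign 106 patients to either the Propofol or Methohexitol groups". At 1:1 allocation that is 53 per arm.

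Section 8.1 gives a different total: "The total sample size will consist of 120 participants (i.e., 60 per treatment arm"). It bases this on 47 per group for 90% power to detect a difference of 0.3 with a two-sided chi-square test at 0.05, and adds: "we anticipate a drop-out rate as high as 20% for this study; therefore, we will enroll a total of 120 subjects".

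The figure of 120 recurs in the monitoring plan (section 10.1: "until our sample size of 120 patients is achieved"; likewise 10.4 and 10.6) and in section 16.2: "We estimate one year may be required in order to recruit and collect data from 120 patients".

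On loss, the end of section 7.2.2 says: "Failure to adhere to this predetermined induction and anesthetic protocol will exclude the patient from further participation in the study". Section 8.3 nevertheless defines the primary analysis as intent-to-treat, in which "all randomized subjects are included according to their randomized treatment arm".

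Section 7.4.3 calls for "variable-size, random permuted blocks" and then fixes the block size at 10.

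**The concern.** The number in 7.2.2 is the one that staff would act on when the lists are made. A list built to it ends 14 patients short of the target in section 8.1. With four strata (gender by ACEI/ARB), a tightly sized list could run out sooner in a common stratum. The trial would then stop short or need an unplanned extension.

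The cost is in the allowance for loss. Section 8.1 provides for 20%, but 106 covers only 11.3%. Loss is a real prospect under this protocol. Sections 3.3.1, 7.2.2 and 19.7 remove patients for a difficult airway, arrhythmia, drug reactions or any departure from the procedure, and section 3.3.2 provides no follow-up of those withdrawn.

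A separate and lesser point does not affect power. The trial is unblinded (7.4.5), and the attending anesthesiologist takes consent (5.1.1.1) and is told each assignment (7.2.2). A fixed block size printed in the protocol could make assignments late in a block predictable to someone who tracks them.

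**Working it through.** **Inputs.** From section 8.1: 47 per group, 90% power, difference 0.30, two-sided chi-square, alpha 0.05, drop-out up to 20%, total 120. From 7.2.2: 106. From 8.2: a propofol rate of 42/51 = 0.82 in an earlier study, with the rate here expected to be slightly higher. No exact rate is given, so 0.85 against 0.55 is an assumption. It is chosen because it returns the plan's 47.

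**Formulas.** Pooled-variance two-proportion test without continuity correction, with p̄ = (p1 + p2)/2:

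- n per arm = [1.96·√(2p̄(1−p̄)) + 1.2816·√(p1(1−p1) + p2(1−p2))]² / (p1 − p2)²
- power = Φ{ [|p1 − p2|·√n − 1.96·√(2p̄(1−p̄))] / √(p1(1−p1) + p2(1−p2)) }

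**Step 1: reproduce the plan's 47.** At 0.85/0.55, p̄ = 0.70, 2p̄(1−p̄) = 0.42, and p1(1−p1) + p2(1−p2) = 0.375. Then n = (1.2702 + 0.7848)²/0.09 = 46.9, so 47. Power at 47 is Φ(1.284) = 90.05%. The plan's figure is reproduced.

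**Step 2: inflate for loss.**

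- 47/0.8 = 58.75, so 59 per arm and 118 in total, which 120 covers.
- Multiplying by 1.2 instead: 47 × 1.2 = 56.4, so 57 per arm and 114 in total.
- Neither route gives 53 per arm (106).

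**Step 3: tolerable loss.** To keep 94 evaluable, 106 allows 1 − 94/106 = 11.3% (12 patients). With 120 it is 1 − 94/120 = 21.7%.

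**Step 4: power at 20% loss.** For 106: 106 × 0.8/2 = 42.4, taken as 42 per arm. For 120: 120 × 0.8/2 = 48 per arm.

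| Rates (propofol / methohexitol) | n for 90% | 106 listed, 42 per arm | 120 listed, 48 per arm | Difference (points) |
|---|---|---|---|---|
| 0.82 / 0.52 | 49.5 | 84.5% | 89.1% | 4.5 |
| 0.85 / 0.55 | 46.9 | 86.5% | 90.7% | 4.2 |
| 0.90 / 0.60 | 41.7 | 90.2% | 93.7% | 3.4 |

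Differences are taken before rounding. At 0.82/0.52 the remaining 0.9 point below 90% comes from the assumed rate and is present at 120 too.

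**Step 5: smaller losses with 106, at 0.85/0.55.** No loss, 53 per arm: 93.2%. Loss of 10%, 47.7 per arm: 90.5%. Loss of 15%, 45 per arm: 88.7%.

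**Step 6: sensitivity.** Counting 85 evaluable patients as 42 and 43 gives 86.8%. Exact power of the chi-square test at 42 per arm is 87.2%. The plan's 47 can also be obtained at 0.82/0.52 with the unpooled formula (46.4, so 47); on that formula power at 42 per arm is 87.0%. Each of these stays below 90%.

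**Block size.** In a permuted block of 2m, the expected number of assignments that are certain given all earlier ones is 2m/(m+1). With m = 5 this is 10/6 = 1.67 of every 10. That is an upper bound. It requires a complete block and someone who tracks every earlier assignment in that stratum.

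**The case against.** The strongest reply is that 106 is a stale figure. It appears once, in a procedural sentence, while the sample-size, monitoring and feasibility sections all say 120. Section 7.4.3, which governs assignment, gives no total, and 106 is not a multiple of the stated block size. Nothing shows that randomisation would actually stop at 106. This is a fair reading of how the number arose. It does not remove the need to correct an operative instruction that contradicts the design.

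Second, power falls below 90% only if 106 is enforced, loss exceeds 11.3%, and the lost patients are missing from the analysis. The endpoint is reached within 15 minutes, and section 8.3 includes everyone randomised. This stands as a limit on the harm: with all 106 analysed, power exceeds 90%. But the 20% allowance is the plan's own, and the removal rules make missing outcomes possible. The tension between those rules and intent-to-treat is a different issue, which would also affect a list of 120.

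Third, the propofol rate is back-solved, and at 0.90/0.60 power stays just above 90%. That is correct, so 86.5% should be read with its range. The loss of 3.4 to 4.5 points due to the shorter list is present throughout that range.

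Fourth, on block size, the documents do not show which description matches the lists. Prediction is also hard with three anesthesiologists and four strata. This is accepted: the point stays secondary and adds nothing to the weight of the main one.

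**Conclusion.** The concern holds. The current text gives two totals for the same randomisation, and only 120 agrees with the plan's 47 per group and 20% drop-out. If 106 were used and 20% were lost, power would be about 86.5% instead of 90.7%. This rests on assumed rates of 0.85 and 0.55 and on the unadjusted chi-square test used for sizing, not the stratified log-binomial model planned for the analysis. The shortfall against 90% is about 3.5 points (about 3 on the less strict counts in Step 6). At 0.85/0.55 it arises only when loss exceeds 11.3%. The correction should be made, but the error does not threaten the validity of the trial. The block-size contradiction is real, minor and separate.

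**What to change.** In section 7.2.2, change 106 to 120. Make each of the four stratum lists long enough to absorb uneven recruitment across strata, and stop randomising at 120 overall.

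Separately, make section 7.4.3 agree with itself and with the lists actually produced. If the lists are not yet made, delete the sentence fixing the block size at 10, keep the variable-size rule, and hold the sizes in the randomisation file, undisclosed to the anesthesiologists. If lists with blocks of 10 already exist, either describe them as they are or generate the remaining assignments with variable sizes; the latter is more than a wording change.

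The main correction costs one number and a check or extension of the lists. It needs no patients beyond the 120 already planned. If enrolment has begun, the lists can be extended without touching assignments already made.

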### 1.3 Secondary Study Endpoints

During the first 15 minutes following anesthetic induction:

- (1) The total number of doses of vasopressors (ephedrine, phenylephrine or vasopressin) administered
- (2) Duration of each hypotension episode
- (3) Refractory hypotension (defined as systolic blood pressure <85mm Hg following 3 doses of vasopressors)
- (4) Systolic blood pressure (at 1 minute intervals)
- (5) Diastolic blood pressure (at 1 minute intervals)
- (6) Heart rate (at 1 minute intervals)
- (7) Blood levels of AVP, All, Epi, NE (at 3, 5, 10 and 15 min)

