### **Both groups**

Following induction in both groups, the blood pressure and heart rate will be measured every one minute for the first 15minutes following the administration of either propofol or methohexitol, and all hemodynamic parameters (systolic blood pressure, diastolic blood pressure, heart rate) will be recorded on the data collection sheet.

Hypotension will be defined as a systolic blood pressure of less than 85 mmHg or greater than 30% decrease in the mean systolic blood pressure (as determined above), whichever is greater. If the patient develops hypotension with a systolic blood pressure of less than 85mm Hg during the 15 minutes following induction of anesthesia, the treatment algorithm outlined below will be followed (Eyraud et al., 1999; Mets, 2013):

One dose of phenylephrine will be administered if heart rate is 60 bpm or above, whereas 5mg of ephedrine will be administered if heart rate is below 60 bpm. The blood pressure will be rechecked 1 minute following, and the process repeated once or twice if necessary. If the

patient is still hypotensive following 3 total doses of vasopressors (phenylephrine and/or ephedrine), they will be considered to be in refractory hypotension and 0.5 Units of vasopressin will be administered. The blood pressure will be rechecked 1 minute following administration of vasopressin. If systolic blood pressure is still less than 85 mmHg, an additional 0.5 Units of vasopressin will be repeated once or twice as needed. Persistent refractory hypotension despite the aforementioned vasopressors will be treated with 4 micrograms of intravenous norepinephrine. All hemodynamic parameters for 15min following anesthetic induction will be recorded by the attending anesthesiologist.

Following anesthetic induction in both study groups, blood samples will be collected (as described above) at 3, 5, 10 and 15 minutes following anesthesia induction. The blood samples will be processed by dedicated research technician as described below.

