For secondary hemodynamic outcomes of systolic blood pressure, diastolic blood pressure and heart rate over the first 15 minutes after treatment initiation, the area under the curve (AUC) for each of these variables will be calculated using the trapezoidal rule. The AUC of each of these variables will be compared between the two treatment groups using linear regression models adjusting for the randomization stratification factors. A linear regression model also will be used to assess differences between the two treatment groups with respect to the duration (in minutes) of hypotension.

Blood will be collected at baseline, 3 min, 5 min, 10 min, and 15 min after treatment initiation to assess changes from baseline in AVP, AI, Epi and NE between the two treatment groups. For these continuous secondary outcomes collected longitudinally, linear mixed-effects models will be fit to compare the two treatment arms with respect to changes in these outcomes over time(Laird and Ware, 1982). The independent variables in the model will be treatment arm, time, the interaction of treatment and time, as well as the randomization stratification factors as covariates. From the mixed-effects models, contrasts will be constructed to test the hypotheses of interest with respect to changes over time in the outcomes. Linear mixed-effects models are an extension of ordinary regression models that account for the between- and within-subject correlation inherent in data involving repeated measurements per subject and allows for the variance-covariance matrix to be explicitly defined.

Following our assessment of the initial fit of the models, we will add covariates to the models that correspond to potential confounders to assess their impact, if any, on the treatment effects. Residual diagnostics will be assessed to determine the appropriateness of the model fit and, if necessary, transformations of the response will be used to meet modeling assumptions. Differences in means and associated confidence intervals (CIs) will be used to quantify the magnitude of the effects for continuous outcomes.

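### The protocol provides for a baseline SBP and heart rate but not a baseline DBP, although DBP is a parallel secondary endpoint analysed by AUC

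*Combined protocol and SAP*

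**What the plan says.** **Baseline.** Under Operating Room Procedures in section 7.2.2, "Baseline blood pressure will be determined by taking three automated successive non-invasive blood pressure measurements every 1-2 minutes", until the systolic values agree within 10%. The next sentence names the values to keep: "The average SBP and accompanying heart rate (HR) of these three measurements will be recorded as mean baseline values". DBP is not among them.

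**After induction.** Under Both groups in section 7.2.2, pressure and heart rate readings are scheduled once a minute for 15 minutes after study drug. Here the text names three variables to keep: "all hemodynamic parameters (systolic blood pressure, diastolic blood pressure, heart rate) will be recorded on the data collection sheet".

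**Endpoints.** Section 1.3 lists SBP, DBP and heart rate as three separate secondary endpoints, each at one-minute intervals over the first 15 minutes.

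**Analysis.** Section 8.3 treats the three alike. For "systolic blood pressure, diastolic blood pressure and heart rate over the first 15 minutes after treatment initiation", it says that "the area under the curve (AUC) for each of these variables will be calculated using the trapezoidal rule". The AUCs are compared with "linear regression models adjusting for the randomization stratification factors". No baseline covariate is named for any of the three, and the section does not say whether a baseline value enters the curve.

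**The concern.** The baseline list has two variables, while the post-induction list, the endpoint list and the analysis list have three. No reason is given. Every other serially measured secondary outcome has a specified baseline: SBP and heart rate through the cuff readings, and the four neurohormones through the preoperative blood sample (sections 7.2.2 and 8.3). The omission therefore looks like an oversight in wording.

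If the text is followed literally, two things are not provided for in DBP: the change from the supine pre-induction value, and adjustment of the DBP comparison for where each patient started. The second matters more, because in a trial of this size the arms can differ at baseline by chance.

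The value cannot be re-measured later. Participation ends 15 minutes after intubation with no follow-up (section 7.3). The clinic DBP implied by exclusion criterion 5 comes from an earlier visit. Retrieval from the clinical record might be possible, but the plan does not provide for it, and patient identifiers are to be destroyed after analysis (section 6.2.1.2).

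**Working it through.** The documents give no figure for the DBP analysis, so there is none to reproduce. The check compares what is specified for each variable and then sizes the consequence.

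**1. Variables side by side**

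| | Baseline specified (7.2.2) | Each minute after induction (7.2.2) | Secondary endpoint (1.3) | AUC (8.3) | Baseline covariate (8.3) | AUC start point (8.3) |
|---|---|---|---|---|---|---|
| SBP | yes | yes | yes | yes | none named | not stated |
| Heart rate | yes | yes | yes | yes | none named | not stated |
| DBP | **no** | yes | yes | yes | none named | not stated |

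DBP differs from the other two in one column only.

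**2. Effect on the AUC itself**

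With readings at minutes 1 to 15, the trapezoidal rule covers 15 − 1 = 14 minutes. With a time-zero value added, it covers 15 minutes, and that value has weight 0.5/15 = 1/30 = 3.3%.

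Illustration (assumed values): DBP constant at 60 mmHg from minute 1, baseline B.

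- Minutes 1 to 15: AUC = 14 × 60 = 840; divided by 14 this is 60.0 mmHg.
- Minutes 0 to 15: AUC = 0.5 × B + 14.5 × 60.
  - B = 70: 35 + 870 = 905; /15 = 60.3 mmHg
  - B = 80: 40 + 870 = 910; /15 = 60.7 mmHg
  - B = 90: 45 + 870 = 915; /15 = 61.0 mmHg

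The time-averaged value moves by 0.3 to 1.0 mmHg. Baseline is taken before study drug, so randomisation gives no expected difference between arms from this source. The lack of a time-zero DBP therefore matters little to the AUC.

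**3. Effect on precision if baseline DBP is a covariate**

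Let r be the correlation between baseline DBP and the DBP AUC. The documents do not give it, so a range is assumed. Residual variance is multiplied by about 1 − r², and the standard error of the treatment difference by about √(1 − r²).

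| r (assumed) | 1 − r² | Variance reduction | √(1 − r²) |
|---|---|---|---|
| 0.3 | 1 − 0.09 = 0.91 | 9% | 0.95 |
| 0.5 | 1 − 0.25 = 0.75 | 25% | 0.87 |
| 0.7 | 1 − 0.49 = 0.51 | 49% | 0.71 |

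**4. Chance imbalance at baseline**

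The standard error of the difference in baseline means, in SD units, is √(2/n) for n per arm. Section 8.1 gives 47 per arm for the power calculation and 60 per arm enrolled: √(2/47) = 0.21 and √(2/60) = 0.18. An imbalance of about 0.2 SD in baseline DBP would be ordinary, and without a recorded value it could be neither seen nor adjusted for.

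**The case against.** The strongest reply is that no planned analysis fails. Section 1.3 asks for DBP at one-minute intervals, not for its change from baseline. Section 8.3 plans change from baseline only for the neurohormones, and its AUC models adjust for the stratification factors alone. The later step in 8.3 that adds potential confounders names no baseline pressure. The mean SBP has its own reason to be listed, since it is the reference for the hypotension definition. All of this stands, and it is why the point is minor.

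Three stronger readings are tempting, and the documents do not support them.

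- *DBP alone lacks a time-zero value.* Section 8.3 assigns no time-zero value to SBP or heart rate either. Their recorded baseline is described before the midazolam and fentanyl step that precedes study drug, so it is not a reading at treatment initiation. Whether it should serve as time zero is open for all three.
- *The three AUCs cover different intervals.* They share one measurement schedule and one AUC rule. As written, all three can run over the same readings from minutes 1 to 15. A mismatch arises only if baseline is added to the SBP and heart rate curves, which the plan does not say.
- *Baseline DBP is never captured.* The cuff step is described as measuring blood pressure, and the data collection sheet is not among the documents. The supportable statement is that the protocol does not specify recording baseline DBP.

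It can also be said that the precision figures belong to a model the plan does not contain. That is correct. They show what recording the value and using it as a covariate would gain; they are not a loss in the planned analysis.

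**Conclusion.** The point holds as a small gap in specification. The protocol names mean SBP and heart rate as recorded baseline values and nowhere names DBP, so DBP is the only haemodynamic AUC outcome without a specified baseline. Change from baseline and baseline adjustment for DBP are therefore not provided for.

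The planned DBP AUC remains feasible, a time-zero reading would carry only 3.3% of its weight, and the primary endpoint, which rests on SBP, is untouched. The possible gain is a residual variance lower by about 9% to 49%. It depends on an assumed correlation of 0.3 to 0.7 and on entering baseline DBP as a covariate. If the data collection sheet already has a baseline DBP field, the data-capture part reduces to aligning the protocol text with the sheet.

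**What to change.** 1. In section 7.2.2, insert DBP after SBP in the sentence on recorded baseline values, so that it lists mean SBP, DBP and heart rate.
2. Confirm that the data collection sheet and the database have a baseline DBP field, and add it if they do not.
3. In section 8.3, name baseline DBP as a covariate in the DBP AUC model, next to the stratification factors. State whether the SBP and heart rate models likewise adjust for their own baselines.
4. In section 8.3, state one AUC start point, either the recorded baseline or minute 1, and apply it to SBP, DBP and heart rate alike. Adding DBP to the baseline list does not settle this by itself. If the baseline is chosen, say that it is the pre-midazolam, pre-fentanyl value.

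The cost is one word and a few lines of text, one form field, and one degree of freedom in the DBP model. The cuff already takes the reading, so no patient procedure is added. The sample size and the primary analysis do not change.
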